#### 4. AMENDMENTS AND UPDATES

Amendment number	Date	Substantial or administrative amendment	Protocol section(s) changed	Summary of amendment(s)	Reason
Amendment 01 (V.2.0)	31Jan2018	Administrative amendment	Author	PPD [REDACTED]	NI Study lead change
		Substantial amendment	Effectiveness Endpoints	- Add 'Hemorrhagic stroke'	Meet to Harmonized Protocol
		Substantial amendment	Safety Endpoints	-Change to 'Major bleeding' - Delete the 'Clinically relevant non-major bleeding'	Meet to Harmonized Protocol
		Administrative amendment	3. ABSTRACT	- Add the information of version, date of protocol, name and affiliation of main author - Add the variables of Exposure - Correct the milestone	Required SOP
		Administrative amendment	5.MILESTONES	Change the milestones which meet SOP required	Required SOP
		Administrative amendment	3. ABSTRACT 7.RESEARCH QUESTION AND OBJECTIVES	Add research questions	Add research questions
		Administrative amendment	8.1 Study design	Add the endpoints	Required SOP
		Substantial amendment	8.2.2 Exclusion criteria	Delete the explains unnecessary Add the exclusion criteria	Delete the explains unnecessary Meet to Harmonized Protocol
		Administrative amendment	8.7. Data Analysis	Add the SOP recommendation words	Required SOP
		Administrative amendment	9.3. Institutional Review Board (IRB)/Independent Ethics Committee (IEC ) 9.4.Ethical Conduct of the Study	Change the SOP required words	Required SOP
Amendment 02 (V.3.0)	03May 2018	Administrative amendment	3. Abstract	Change the phrases of Research question and objectives	Amend protocol phrases consistently with SAP.
		Administrative	7. Research question and	Change the phrases of Research	Amend protocol phrases consistently

Amendment number	Date	Substantial or administrative amendment	Protocol section(s) changed	Summary of amendment(s)	Reason
		amendment	objectives 8.1 Study design 8.2 Setting	question and objectives	with SAP.
		Administrative amendment	8.2.2 Exclusion criteria	Delete 'Hip or knee replacement' from #5.	Duplicate from exclusion criteria #1.
		Substantial amendment	8.3 Variables	Change the operational definitions	Redefinition of hemorrhagic stroke, ischemic stroke and systemic embolism
				Delete the variable of 'myocardial infarction' from effectiveness outcome.	Redefinition of effectiveness outcome
				Add variable of 'Individual outcome of major bleeding'	Redefinition of each major bleeding events
				Delete variables of 'Dose', 'Medical history' and 'Study drugs'	Delete unnecessary sections.
				Add codes on operational definitions of 'Valvular AF/ Prosthetic heart valves' and 'Hip or knee replacement'	Add procedure codes.
		Substantial amendment	8.7	Additional sensitivity analysis	Perform IPTW using the propensity score derived from multinomial model

## 5. MILESTONES

Milestone	Planned date
Completion of feasibility assessment	10 Apr 2017
Start of data collection	01 Feb 2018
End of data collection	31 Nov 2018
Interim report 1	30 Jun 2018
Interim report 2	31 Dec 2018
Final study report	28 Feb 2019

## 6. RATIONALE AND BACKGROUND

Atrial fibrillation (AF) is the most common persistent arrhythmia, and its prevalence has been estimated to be 1-2% of the general population, with a progressive increase in thromboembolic events and death (1). AF increases the risk of ischemic stroke by five-fold and is associated with 15% of stroke for all age groups and 30% in patients aged 80 years and older (2). Patients with AF-related ischemic stroke have higher recurrent risk, morbidity, and mortality as compared to patients with other types of stroke (3). Thus, current clinical guidelines for AF emphasize stroke prevention in patients with AF, in the presence of stroke risk factors (4). Effective stroke prevention essentially requires oral anticoagulants (OAC) therapy. Vitamin K antagonists (i.e., warfarin) effectively decrease the risk for thromboembolic events in patients with AF (5). However, vitamin K antagonists have several limitations, including need for regular blood monitoring and possibility for food or drug interactions. This had led to the quest for new OACs that would be more safe and effective than warfarin (6). In randomized controlled trials, NOACs demonstrated noninferior or superior reduction in stroke and systemic embolism when compared to warfarin (7-10).

Physicians now have a choice between the available NOACs but have relatively little evidence to guide their decision-making because of no head-to-head trials of these drugs. In addition, there have been few studies on efficacy and safety outcomes of NOACs. The nationwide claims database in Korea can provide an opportunity to study comparative effectiveness and safety outcomes of NOACs in patients with atrial fibrillation in Korea.

## 7. RESEARCH QUESTION AND OBJECTIVES

Research question: What is the real world data on antiplatelet therapy, warfarin and NOACs that can be found in the nationwide claims database in Korea?

Primary objectives

1. To explore baseline characteristics and drug utilization patterns in patients with nonvalvular atrial fibrillation (NVAF) who newly initiated NOACs, warfarin, or used aspirin
2. To compare effectiveness including hemorrhagic stroke, ischemic stroke, and systemic embolism of antithrombotic therapies in patients with NVAF with the following antithrombotic therapies: NOACs, warfarin, and aspirin
3. To compare safety including major bleeding of antithrombotic therapies in patients with NVAF with the following antithrombotic therapies: NOACs, warfarin, and aspirin

*[NOTE] Comparative analyses will be performed contingent on a feasibility assessment based on the descriptive analyses*

[figure not shown]
Secondary objectives

1. To explore and understand more detailed drug utilization patterns
  - o Standard doses versus low dose of NOACs
  - o Patterns of usage (i.e., switching, discontinuation) and clinical events preceding the pattern
  - o Compliance (i.e., medication possession ratio)
2. To compare effectiveness and safety of antithrombotic therapies versus not using therapies among low risk patients (low score of CHA2DS2-VASc)

## 8. RESEARCH METHODS

### 8.1 Study design

This study will use a retrospective cohort design in which the treatment effectiveness and safety outcomes of new use of NOACs compared to other NOACs, new use of warfarin, and aspirin will be evaluated in patients with atrial fibrillation using the Korean Health Insurance Review & Assessment Service (HIRA) database. Comparative analyses will be performed contingent on a feasibility assessment based on the descriptive analyses. Propensity score method and Cox proportional hazards models will be used to account for selection bias, differences in follow-up time, and right data censoring. This will allow us to minimize selection bias and confounding bias and provide outcome data amenable to rapid clinical interpretation (i.e., time-to-event analysis, hazard ratios). Furthermore, HIRA database will allow us to preserve the population-based longitudinal data collection advantages. The overall study design is described in Figure 1.

**Figure 1. Study design scheme**

## 8.2 Setting

### 8.2.1 Inclusion criteria

Patients must meet all of the following inclusion criteria to be eligible for inclusion in the study:

1. Patients aged 18 years or older on the index date
2. Patients had  $\geq 1$  medical claim for AF (refer to Table 1) before or on the index date with at least one hospitalization or at least two outpatient visits:

**Table 1. Diagnosis codes for inclusion criteria.**

KCD-6 	KCD-7 
I48 (Atrial fibrillation and flutter)	I48 (Atrial fibrillation and flutter)
I480 (Atrial fibrillation)	I480 (Paroxysmal atrial fibrillation)
I481 (Atrial flutter)	I481 (Persistent atrial fibrillation)
	I482 (Chronic atrial fibrillation)
	I483 (Typical atrial flutter)
	I484 (Atypical atrial flutter)
	I489 (Atrial fibrillation and atrial flutter, unspecified)

KCD-6, Korean version of ICD-10 (6th revision); KCD-7, Korean version of ICD-10 (7th revision)

1) KCD-6 diagnosis codes will be used from 1 July 2015 to 31 December 2015.

2) KCD-7 diagnosis codes will be used from 1 January 2016 to 30 November 2016.

[NOTE] KCD code is based on ICD-10 and almost similar, but KCD code is slightly different from ICD-10 (e.g., ICD-10 is more subdivided and extensive than KCD code).

3. Patients prescribed aspirin, warfarin, or NOACs during intake period (from July 1, 2015 to November 30, 2016)

*[Note] NOACs include apixaban, dabigatran, and rivaroxaban.*

### 8.2.2 Exclusion criteria

Patients meeting any of the following criteria will not be included in the study.

1. Medical claims indicating diagnosis or procedure for hip/knee replacement surgery within 6 weeks prior to index date
2. Medical claims indicating a diagnosis code indicative of rheumatic mitral valvular heart disease, mitral valve stenosis during the 12-month baseline period  
(Valvular AF / Prosthetic heart valves)
3. Medical claims indicating a diagnosis code of VTE (Venous thromboembolism) during the 12-month baseline period
4. Medical claims indicating a diagnosis or procedure code of transient AF, or cardiac surgery during the 12-month baseline period

(Thyrotoxicosis, Hypertrophic cardiomyopathy, Elective defibrillation, radiofrequency ablation, or left atrial appendage occlusion)

5. Medical claims indicating a diagnosis code of other conditions during the 12-month baseline period  
(End-stage chronic kidney disease / Kidney transplant / Dialysis / Pericarditis)
6. For the comparison of “NOAC versus NOAC”, and “NOAC versus warfarin”, patients with any OACs (apixaban, dabigatran, rivaroxaban, or warfarin) in the pre-index period (from 1 year prior to the day before index date)
  - *[NOTE] Patients prescribed antiplatelets in the pre-index period will not be excluded.*
7. For the comparison of “NOAC versus aspirin”, patients with following medications in the pre-index period (from 1 year prior to the day before index date)
  - NOAC user: OACs (apixaban, dabigatran, rivaroxaban, warfarin)
  - Aspirin user: none
  - *[NOTE] NOAC user is defined as OAC naïve user and aspirin user is allowed to have OACs or antiplatelets in the pre-index period.*

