## 8.6 Data management

### Obtaining data files

Pusan National University team will submit the data request form to HIRA. After the HIRA committee review, the data will be uploaded in the server. The study team will access the data through the remote access using IP address. All medical or pharmacy claims and demographic information from January 1, 2007 to November 30, 2016 of patients with atrial fibrillation (KCD code: I48) from July 1, 2015 to November 30, 2016 will be accessed.

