3 ANALYSIS SETS/ POPULATIONS

3.1 FULL ANALYSIS SET

Inclusion criteria

Patients must meet all of the following inclusion criteria to be eligible for inclusion in the study:

1. Patients aged 18 years or older on the index date
2. Patients had ≥ 1 medical claim for AF (refer to Table 1) before or on the index date with at least one hospitalization or at least two outpatient visits:

[Diagnosis codes for inclusion criteria]

KCD-6 ¹⁾	KCD-7 ²⁾
I48 (Atrial fibrillation and flutter)	I48 (Atrial fibrillation and flutter)
I480 (Atrial fibrillation)	I480 (Paroxysmal atrial fibrillation)
I481 (Atrial flutter)	I481 (Persistent atrial fibrillation)
	I482 (Chronic atrial fibrillation)
	I483 (Typical atrial flutter)
	I484 (Atypical atrial flutter)
	I489 (Atrial fibrillation and atrial flutter, unspecified)

KCD-6, Korean version of ICD-10 (6th revision); KCD-7, Korean version of ICD-10 (7th revision)

1) KCD-6 diagnosis codes will be used from 1 July 2015 to 31 December 2015.

2) KCD-7 diagnosis codes will be used from 1 January 2016 to 30 November 2016.

[NOTE] KCD code is based on ICD-10 and almost similar, but KCD code is slightly different from ICD-10 (e.g., ICD-10 is more subdivided and extensive than KCD code).

3. Patients prescribed aspirin, warfarin, or NOACs in intake period (from July 1, 2015 to November 30, 2016)
[Note] NOACs include apixaban, dabigatran and rivaroxaban.

Exclusion criteria

Patients meeting any of the following criteria will not be included in the study.

1. Medical claims indicating diagnosis or procedure for hip/knee replacement surgery within 6 weeks prior to index date
2. Medical claims indicating a diagnosis code indicative of rheumatic mitral valvular heart disease, mitral valve stenosis during the 12-month baseline period
(Valvular AF / Prosthetic heart valves)
3. Medical claims indicating a diagnosis code of VTE (Venous thromboembolism) during the 12-month baseline period
4. Medical claims indicating a diagnosis or procedure code of transient AF, or cardiac surgery during the 12-month baseline period
(Thyrotoxicosis, Hypertrophic cardiomyopathy, elective defibrillation, radiofrequency ablation, or left atrial appendage occlusion)
5. Medical claims indicating a diagnosis code of others during the 12-month baseline period
 - (End-stage chronic kidney disease / Kidney transplant / Dialysis / Pericarditis)

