 - A. Sub-dataset 7: patients with index treatment of apixaban and patients with index treatment of aspirin
 - B. Sub-dataset 8: patients with index treatment of dabigatran and patients with index treatment of aspirin
 - C. Sub-dataset 9: patients with index treatment of rivaroxaban and patients with index treatment of aspirin

[NOTE] The index date will be defined as date of the first prescription of NOAC or aspirin in patients with NVAF during the intake period (from July 1, 2015 to November 30, 2016). To identify NOAC users, a look-back observation period from 1 year prior to the day before the index date will be used and must indicate no OAC use during this period. However, OAC use or antiplatelet use during a look-back observation period from 1 year prior to the day before the index date will be allowed for aspirin users. The diagnosis date of NVAF could occur from January 1, 2007 up to and including the index date.

Each patient was followed until discontinuation or switching of index treatment, outcome occurrence, or study ends (November 30, 2016).

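### Prosthetic valves and past valve surgery exclude a patient only if coded in the 12 months before index, although claims back to 2007 are held

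*Protocol*

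**What the plan says.** Protocol 8.2.2 item 2 (repeated in SAP 3.1) excludes patients with claims for rheumatic mitral valve disease or "mitral valve stenosis during the 12-month baseline period"; the bracketed label is "Valvular AF / Prosthetic heart valves". The codes are in the exclusion row of Protocol 8.3 and in SAP Table 13:

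- diagnosis categories I05, I08, I09, I34 and Q23;
- T820 and T826;
- prosthetic-valve status codes Z952 to Z954;
- a list of Korean valve procedure codes.

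Neither list gives a different time window.

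Item 5 has the same limit: "Medical claims indicating a diagnosis code of other conditions during the 12-month baseline period", covering "End-stage chronic kidney disease / Kidney transplant / Dialysis / Pericarditis". Kidney transplant is identified by the status code Z940 alone.

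The data held go back much further. Protocol 8.6 provides for access to "All medical or pharmacy claims and demographic information from January 1, 2007 to November 30, 2016". SAP 3.1 lets the AF diagnosis date from 1 January 2007 up to the index date.

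For NOAC versus aspirin (sub-datasets 7 to 9), NOAC users must have had no oral anticoagulant in the preceding year. For aspirin users, "OAC use or antiplatelet use during a look-back observation period from 1 year prior to the day before the index date will be allowed".

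**The concern.** Up to nine years or more of history can bring a patient into the cohort, but only one year can take the patient out. A prosthetic valve or a past valve operation is a lasting state. The surgical procedure code is billed once, so after 12 months the exclusion depends on a diagnosis or status code being recorded again.

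Two features could make this more than a labelling matter:

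- **Arms may differ.** A valve patient anticoagulated in the past year is removed from the NOAC arm by the anticoagulant-naive rule but can stay in the aspirin arm. SAP Table 3 itself gives valvular AF as an example of a contraindication that may precede stopping or switching, so the plan accepts that valve status bears on treatment.
- **The named covariates do not cover it.** Valve disease and prosthetic valves are absent from SAP Table 4 and from the comorbidities in the Table 5 shell. The final propensity-score covariate list is still open (SAP 5.1), but as listed it would not balance these patients directly.

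No reason for 12 months, no longer look-back as a sensitivity analysis and no mention in Protocol 8.9 could be found.

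**Working it through.** The plan gives no figure for this point to reproduce. The anticipated 150,000 patients (Protocol 8.5) come from HIRA counts of 148,130 and 169,259, before exclusions. That figure is used here only for scale.

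**1. Look-back available and used.** Claims start on 1 January 2007; index dates run from 1 July 2015 to 30 November 2016.

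- Earliest index date: 3,103 days / 365.25 = 8.5 years.
- Latest index date: 3,621 days / 365.25 = 9.9 years.
- Used: 365 days. Unused: (3,103 − 365) / 365.25 = 7.5 years to (3,621 − 365) / 365.25 = 8.9 years.

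**2. Who passes the rule.** Take a valve operation in 2010 and an index date in 2016. The procedure code lies outside the window. If no listed diagnosis or status code falls in the last 12 months, the patient is not excluded. One such code on any claim in that year is enough to exclude.

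**3. How many (illustration only).** Let p be the share of patients with a lasting condition on the lists and m the share of those with no qualifying code in the last year. Neither is in the documents; both are assumed. Patients retained = N × p × m. Their share of the remaining cohort = p·m / (1 − p(1 − m)). N = 150,000.

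| p | m | Retained | Share |
|---|---|---|---|
| 0.5% | 5% | 38 | 0.00025 / 0.99525 = 0.03% |
| 2% | 10% | 300 | 0.002 / 0.982 = 0.20% |
| 5% | 30% | 2,250 | 0.015 / 0.965 = 1.6% |

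Here p covers every lasting condition, including the broad diagnosis categories, so these counts overstate what the prosthetic-valve and procedure codes alone would remove.

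**4. Effect on the hazard ratio (illustration only).** Let f_n and f_c be the retained shares in the NOAC and comparator arms, and R the event rate of retained patients relative to the rest. All three are assumed. The hazard ratio is multiplied by about (1 + f_n(R − 1)) / (1 + f_c(R − 1)).

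| f_n | f_c | R | Multiplier |
|---|---|---|---|
| 0.05% | 0.05% | any | 1.000 |
| 0.1% | 0.5% | 1.5 | 1.0005 / 1.0025 = 0.998 |
| 0.2% | 1% | 2 | 1.002 / 1.010 = 0.992 |
| 0.5% | 2% | 3 | 1.010 / 1.040 = 0.971 |

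The comparator share is allowed to exceed the cohort-wide range because the leak may concentrate in the aspirin arm. With R above 1 and more retained patients on aspirin, the shift favours the NOAC.

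**The case against.** The 12-month window is a defensible choice. It is the same length for every patient, whereas a full look-back varies by index date. Protocol 8.9.3 says continuous enrolment cannot be ensured, which favours a short common window. The broad categories (I05, I08, I09, I34, Q23) need only one claim, so running them over 8.5 to 9.9 years would also exclude patients on old or mistaken codes. Status codes and chronic diagnoses may be billed again and catch many of the patients at issue. Table 1 dates its KCD versions only from July 2015, so earlier coding needs checking. The amendment log gives alignment with a harmonised protocol as a reason for added exclusions, so a local change may cost some comparability. Protocol 8.9.1 also concedes coding error in general, though it does not mention the look-back.

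Most of this stands for the broad diagnosis categories, which is why they are better placed in a sensitivity analysis. It has little force for prosthetic-valve and valve-surgery codes: they mark a lasting state, and a look-back of unequal length does little harm there.

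A reader might infer four stronger points that the documents do not support:

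- *The retained patients breach the criteria.* They satisfy the criteria as written; the mismatch is with the nonvalvular population the study names.
- *Transplant is lost in the same way as surgery.* Transplant has no procedure code on either list, only Z940, and it does not make AF valvular.
- *Hypertrophic cardiomyopathy needs the same change.* It belongs to item 4, headed as transient AF or cardiac surgery, and nothing here argues for moving it.
- *Uneven accumulation between arms is established.* It is plausible from the cohort rules, but not shown.

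**Conclusion.** The point holds for prosthetic valves and past valve surgery. Protocol and SAP agree on 12 months, the earlier claims are held, and a valve operation more than a year old with no later valve code is analysed as NVAF. The leak may be larger in the aspirin arm, so NOAC versus aspirin is the comparison most exposed.

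The number of patients is unknown. With p from 0.5% to 5% and m from 5% to 30%, it is 38 to 2,250 of 150,000. With retained shares of 0.1% to 0.5% in the NOAC arm against 0.5% to 2% in the comparator, and R from 1.5 to 3, the hazard ratio is multiplied by about 0.97 to 1.00; with equal shares it does not move. All these inputs are assumptions. On this scale the gap is a low-cost refinement of the population definition and no reason to doubt the main comparisons.

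**What to change.** - **Main rule.** In Protocol 8.2.2 item 2, SAP 3.1 and both code lists, apply Z952 to Z954, T820, T826 and the listed valve procedure codes to all claims from 1 January 2007 to the index date. Item 2 speaks only of diagnosis codes while the lists add procedures; the amended sentence should cover both.
- **Other conditions.** Keep the 12-month window.
- **Sensitivity analysis.** Repeat the comparisons with the full look-back for I05, I08, I09, I34, Q23 and kidney transplant (Z940).
- **Reporting.** Give the additional exclusions by arm in each sub-dataset, which replaces the assumed sizes above with real counts.

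**Cost.** A date limit in the program, a line in each document and one extra sensitivity run; no new data request. The cohort becomes slightly smaller and the look-back varies from 8.5 to 9.9 years. The procedure codes must be checked for validity in earlier years, including the entry printed as 1740 without a letter in both lists.

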#### ***Secondary objectives***

1. To explore and understand more detailed drug utilization patterns
  - o Standard doses versus reduced doses of NOACs

- Patterns of usage (i.e., switching, discontinuation) and clinical events preceding the pattern
- Compliance (i.e., medication possession ratio)

2. To compare effectiveness and safety of antithrombotic therapies versus not using therapies among low risk patients (low score of CHA2DS2-VASc)

**Study design:** Retrospective cohort study

**Population:** Subjects with atrial fibrillation diagnosed (from January 1, 2007 up to and including the index date\*) who newly initiated antithrombotic therapies (NOACs (not including edoxaban), warfarin, or used aspirin) between July 1, 2015 and November 30, 2016 in the Korean Health Insurance Review & Assessment Service (HIRA) database

*\*Index date is the first prescription date of study drugs, including NOACs, warfarin, and aspirin during the intake period (from July 1, 2015 to November 30, 2016).*

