6. For the comparison of “NOAC versus NOAC”, and “NOAC versus warfarin”, patients with any OACs (apixaban, dabigatran, rivaroxaban, or warfarin) in the pre-index period (from 1 year prior to the day before index date)
 - *[NOTE] Patients prescribed antiplatelets in the pre-index period will not be excluded.*
7. For the comparison of “NOAC versus aspirin”, patients with following medications in the pre-index period (from 1 year prior to the day before index date)
 - NOAC user: OACs (apixaban, dabigatran, rivaroxaban, warfarin)
 - Aspirin user: none
 - *[NOTE] NOAC user is defined as OAC naïve user and aspirin user is allowed to have OACs or antiplatelets in the pre-index period.*

Cohorts

To avoid increasing type I error when multiple comparisons occur, this full analysis set will be splitted into multiple sub-analysis sets as follows:

1. NOAC vs NOAC (both as OAC naïve users)
 - A. Sub-dataset 1: patients with index treatment of apixaban and patients with index treatment of dabigatran
 - B. Sub-dataset 2: patients with index treatment of apixaban and patients with index treatment of rivaroxaban
 - C. Sub-dataset 3: patients with index treatment of dabigatran and patients with index treatment of rivaroxaban

[NOTE] The index date will be defined as date of the first prescription of NOAC in patients with NVAF. To identify new users, a look-back observation period from 1 year prior to the day before the index date will be used and must indicate no OAC use during this period. The diagnosis date of NVAF could occur from January 1, 2007 up to and including the index date.

2. NOAC vs warfarin (both as OAC naïve users)
 - A. Sub-dataset 4: patients with index treatment of apixaban and patients with index treatment of warfarin
 - B. Sub-dataset 5: patients with index treatment of dabigatran and patients with index treatment of warfarin
 - C. Sub-dataset 6: patients with index treatment of rivaroxaban and patients with index treatment of warfarin

[NOTE] The index date will be defined as date of the first prescription of NOAC or warfarin in patients with NVAF. To identify new users, a look-back observation period from 1 year prior to the day before the index date will be used and must indicate no OAC use during this period. The diagnosis date of NVAF could occur from January 1, 2007 up to and including the index date.

3. NOAC (OAC naïve user) vs aspirin (no restrictions of antiplatelet or OAC use in the pre-index period)

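### AF codes on the index date count for inclusion, but no exclusion is stated to cover that date, so a same-day VTE start can enter as an NVAF new user

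*Protocol*

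**What the plan says.** **Inclusion.** Protocol 8.2.1 item 2 counts AF claims "before or on the index date with at least one hospitalization or at least two outpatient visits". SAP 3.1 gives the look-back as "The diagnosis date of NVAF could occur from January 1, 2007 up to and including the index date". Protocol 8.6 limits the extract to claims "of patients with atrial fibrillation (KCD code: I48) from July 1, 2015 to November 30, 2016 will be accessed", so every patient also carries an I48 claim in that window.

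**Exclusions.** In Protocol 8.2.2, item 1 covers "hip/knee replacement surgery within 6 weeks prior to index date". Item 3 covers "Medical claims indicating a diagnosis code of VTE (Venous thromboembolism) during the 12-month baseline period". Items 2, 4 and 5 (valvular disease, transient AF and cardiac procedures, renal disease and pericarditis) use the same 12-month baseline period. Items 6 and 7 concern prior drug use only and apply "in the pre-index period (from 1 year prior to the day before index date"). SAP 3.1 repeats these windows.

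**Index date.** The Protocol abstract says: "Index date is the first prescription date of study drugs, including NOACs, warfarin, and aspirin during the intake period". Nothing ties that prescription to AF as its indication.

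**The concern.** VTE and recent joint replacement are reasons to start an anticoagulant other than AF. Because the index date is simply the first study-drug prescription, these exclusions are the plan's only protection against counting such a start as stroke prevention. A competing indication may well be coded on the day the drug is first prescribed. If the exclusion window ends the day before, it misses the patients whose index prescription was written for the excluded condition, while an AF code on the same claim still counts towards inclusion.

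At stake is misclassified indication. Patients in the acute phase of VTE may differ in bleeding risk and treatment course. They would sit mainly in the OAC arms and possibly in different shares by drug. The resulting distortion is systematic, so a large sample does not remove it.

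**Working it through.** **Windows side by side**

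| Rule | Place | Last day covered |
|---|---|---|
| AF claim | Protocol 8.2.1 item 2; SAP 3.1 | Index date, explicit |
| Hip/knee replacement | Protocol 8.2.2 item 1 | Before the index date, on plain wording |
| Valvular disease, VTE, transient AF and procedures, renal disease and pericarditis | Protocol 8.2.2 items 2 to 5 | Not stated in the available text |
| Prior OAC use | Protocol 8.2.2 items 6 and 7 | Day before index, explicit |

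Two things point to the baseline period being the pre-index period. The pre-index period is the only one-year look-back with a written end day. Protocol 8.4 and SAP 2.1 also measure baseline health status over it. A programmer would probably code the two as one, which leaves the index date uncovered for items 2 to 5.

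**Worked case on that reading.** Two outpatient AF visits in 2011; pulmonary embolism (I26) first coded on 10 March 2016, with rivaroxaban or warfarin prescribed that day and no OAC in the previous year; one I48 claim between July 2015 and November 2016.

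1. The AF criterion is met through two outpatient visits.
2. The extract rule is met through the I48 claim in the window.
3. Item 3 finds no VTE code before 10 March, and items 6 and 7 find no prior OAC.
4. The patient enters as an NVAF new user. With the VTE code dated one day earlier, the patient is excluded.

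The footnotes to Protocol Table 1 date the AF code versions only from 1 July 2015, which does not fit the look-back to 2007 and should be reconciled. The case does not depend on this: the two visits could equally fall after that date.

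**Covariates.** SAP Table 4 has no VTE variable. Of the VTE codes in SAP Table 13, I26 and those under I80 to I82 appear in none of the scores in SAP Tables 9 to 11. The cerebral venous codes I636 and I676 do fall within stroke or cerebrovascular items there. The final propensity covariate list is left open in SAP 5.1, but nothing planned captures a VTE code first recorded on the index date.

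**Overlap with the outcome.** I636 is a VTE exclusion code and also falls under the ischemic stroke outcome code I63. Follow-up starts on the index date (Protocol 8.3). An index-date I636 with hospitalization and brain imaging could therefore be both a missed exclusion and a day-0 primary event.

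**Size.** The plan gives no figure to reproduce, so these inputs are assumptions: p is the share of an arm that are same-day VTE starts, k is their bleeding rate relative to other starters, rates are constant, and there is no drug effect. The arm's rate is then multiplied by (1 − p) + pk = 1 + p(k − 1).

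With none in the comparator, the apparent hazard ratio is 1 + p(k − 1):

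- p = 0.01, k = 2: 1 + 0.01 × 1 = 1.01
- p = 0.03, k = 3: 1 + 0.03 × 2 = 1.06
- p = 0.05, k = 3: 1 + 0.05 × 2 = 1.10

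With both arms affected, it is [1 + pA(k − 1)] / [1 + pB(k − 1)]. For 3% versus 2% and k = 3, this is 1.06 / 1.04, or about 1.02.

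**The case against.** **The end day for items 2 to 5 is inferred.** A reader might conclude that all the exclusion windows demonstrably stop before the index date. The documents support that only for item 1. Items 2 to 5 use a different term from items 6 and 7, and Figure 1, which is not shown, may define it. This stands. What remains is that the eligibility text gives an end day for prior drug use and none for diagnoses.

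**Day-level dates may not exist.** Protocol 8.4 describes medical claims as dated by month and year. If so, a same-day code cannot be told from one a day earlier, and changing a date comparison will not be enough. This also stands, but it means that same-month codes have no rule at present, which adds to the need for one.

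**An old AF code is not sufficient.** Correct: the patient needs a hospitalization or two outpatient visits for AF, plus an I48 claim in July 2015 to November 2016. Such patients do carry a current AF diagnosis. That does not make AF the reason for the index prescription.

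**The premises on timing and risk have no source in the documents.** Neither document says how often a competing indication is coded on the prescription day, or gives the relative bleeding rate. The figures above are illustrations.

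**The argument does not carry over to every exclusion.** Item 4 includes cardioversion, ablation and appendage occlusion, and SAP Table 3 treats these as procedures for AF. They are not competing indications, and extending that window would change the target population. Valvular and end-stage kidney disease are likewise not shown to prompt an index-day start. This stands.

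**Conclusion.** The concern holds for the competing-indication exclusions: VTE (item 3) and joint replacement (item 1). AF inclusion explicitly reaches the index date, no exclusion explicitly does, and the natural reading admits a same-day VTE start as an NVAF new user. The VTE part rests on equating the baseline period with the pre-index period; the joint-replacement part rests on plain wording.

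The size is unknown, because the documents give no count. Under the assumed shares and rates, the shift in the null hazard ratio for major bleeding is 1.01 to 1.10 only if the comparator has no such patients, which is plausible at most for the three aspirin sub-datasets (7 to 9). Six of the nine sub-datasets (1 to 6) compare one OAC with another, where the shift is smaller and depends on the difference in shares. A reader might infer a bias of up to 10% across all comparisons; the documents do not support that. The change is still worth making before outcomes are analysed, because the remedy is simple and the affected count can be read from data already requested.

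**What to change.** In Protocol 8.2.2 and SAP 3.1:

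1. Define the first and last day of the 12-month baseline period.
2. Make item 3 (VTE) and item 1 (joint replacement) run up to and including the index date, or through the index month if medical claims carry only month and year.
3. State explicitly how index-date codes are treated for items 2, 4 and 5, without extending those windows by default.
4. Keep the drug washout in items 6 and 7 ending the day before index, as a new-user design requires.
5. Before any outcome analysis, report by drug how many patients have an exclusion code on the index date (or in the index month).

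The cost is a short text change in both documents, a revised date rule in the programs, and a small loss of patients. If dates are monthly, a few patients whose VTE followed the index date within the same month may also be excluded. No new data are needed.
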